**PROTOCOL SUMMARY**

Title:	A Prospective, Randomized, Open-label Clinical Trial to Assess the Safety and Immunogenicity of Simultaneous versus Sequential Administration of tetanus toxoid, reduced diphtheria toxoid, and acellular pertussis vaccine and inactivated influenza vaccine in Pregnant Women – Pilot
Phase:	Phase 4
Population:	80 adult pregnant women (18-45 years) at $\geq$ 26 weeks 0 days gestation through $\leq$ 32 weeks 0 days gestation who plan on receiving Tdap and IIV during the current pregnancy in accordance with the Advisory Committee on Immunization Practices (ACIP) and American College of Obstetricians & Gynecologists (ACOG) national recommendations.
Clinical Sites:	Two: Duke University (Lead); Cincinnati Children's Hospital Medical Center (Contributor)
Study Duration:	24 months (4 months to recruit/enroll (per flu season), maximum of 26 weeks to follow (5.5 months) (per flu season), 4.5 months to perform analysis and laboratory assays (per flu season))
Participant Duration:	Up to 23 weeks depending upon gestational age at enrollment and delivery
Description of Study Procedures:	
This is a pilot, prospective, randomized, open-label clinical trial. During the study, pregnant women will be randomized (1:1) to receive co-administration of a single intramuscular (IM) 0.5 mL dose of US-licensed inactivated influenza vaccine (IIV) and a single intramuscular (IM) 0.5 mL dose of US-licensed Tetanus toxoid, reduced diphtheria toxoid and acellular pertussis vaccine adsorbed (Tdap) or sequential administration of the vaccines (IIV followed by Tdap ~ 21 days later). Vaccines will be administered by licensed study personnel.
 
Prior Tdap/Td/TT and influenza vaccine history will be verified by medical record review when possible.
 
Injection-site (local) and systemic reaction data will be assessed on vaccination day and during the 7 days following vaccination using either identical web-based or paper diaries, depending on study participant preference.
 
Maternal serum samples will be collected for antibody titers relevant to the Tdap and Influenza at time points that include: prior to vaccination(s), ~22 days post vaccination(s), and at

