administered simultaneously in 8464 pregnancies and sequentially (in any order) in 28,380 pregnancies. The VSD study concluded that simultaneous administration of Tdap and IIV vaccines during pregnancy was not associated with a higher risk of medically attended adverse acute outcomes or birth outcomes compared with sequential vaccination. While this is certainly informative given the current paucity of data, it did not provide data on reactogenicity events that did not lead to a medical visit, such as maternal fever or injection-site pain. Another limitation of a retrospective study like the VSD analysis is that it did not allow for assessment of immunogenicity, or vaccine-induced antibody response and seroprotection against the vaccine-preventable disease. Some investigators on our study team participated in a randomized, placebo-controlled trial of Tdap given at 32 weeks gestation vs. immediately postpartum in which we followed infants for the first year of life. We found that antenatal Tdap resulted in high pertussis antibody levels in infants during the first 2 months of life and did not substantially affect infant immune responses to pediatric DTaP. Such data have been used to support the ACIP recommendation to administer Tdap during every pregnancy. However, recent studies raise concerns about the impact on pertussis immunogenicity following co-administration of IIV and Tdap. Two studies in non-pregnant adults suggest that simultaneous vs. sequential administration (IIV followed by Tdap 4-6 weeks later) is safe and well-tolerated. However, one of the studies demonstrated higher reports of injection-site pain after simultaneous administration. Furthermore, both studies suggested a diminished antibody response to pertussis antigens following simultaneous administration of IIV and Tdap as compared to sequential dosing, and some investigators on our study team have demonstrated reduced antibody responses to influenza vaccine (as measured by hemagglutinin inhibition) in pregnant women compared to non-pregnant women. This suggests that decreased immune responses may be exacerbated in pregnant women, though the clinical importance remains unclear in the adult population. These findings raise questions about the potential impact of simultaneous administration during pregnancy. Given that the primary motivation for administering Tdap during pregnancy is to boost maternal antibodies against pertussis and attempt to achieve the highest possible antibody titer at the time of delivery, diminished anti-pertussis antibody production could result in a shorter duration of protection against pertussis in vulnerable young infants.

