## 3 STUDY DESIGN

### 3.1 Main study design

This pilot study is a prospective, randomized open-label clinical trial of approximately 80 healthy pregnant women enrolled at Duke University Medical Center (Lead Contractor) and Cincinnati Children's Hospital (Contributing Contractor) who will be followed after they receive simultaneous or sequential single 0.5 mL intramuscular (IM) dose of US-licensed inactivated influenza vaccine (quadrivalent Fluzone) and single 0.5 mL intramuscular (IM) dose of US-licensed tetanus toxoid, reduced diphtheria toxoid and acellular pertussis vaccine (Tdap, Boostrix). In each study participant, the Tdap and IIV vaccine that is administered will be produced by different manufacturers unless there are manufacturing issues or vaccine shortages that necessitate acquisition of Tdap and IIV from the same manufacturer.

Pregnant women 18-45 years of age and 26-32 weeks gestation will be enrolled over a period of approximately 4 months per flu season. The purpose of the study is to compare the rates of injection-site and systemic reactions and the immune response following simultaneous administration of IIV and Tdap or sequential administration of IIV followed by Tdap in pregnant women, and to assess rates of adverse pregnancy (maternal and infant) outcomes including, but not limited to, preterm birth, small for gestational age (SGA), and chorioamnionitis. Maternal and infant outcomes will be collected by medical record review from enrollment through hospital discharge following delivery.

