## 7 STATISTICAL CONSIDERATIONS

In collaboration with the CDC and Cincinnati sites, the research team at Duke will oversee the statistical analysis. This pilot study is not designed based on statistical considerations regarding power/sample size in relation to group comparisons. Therefore, descriptive statistics and confidence intervals for continuous variables will be presented (e.g., mean, standard deviation, median, interquartile range, and confidence boundaries). Categorical variables will be summarized with frequencies, percentages, and exact confidence boundaries.

For analysis, data will reside on a secure Duke server maintained by Duke Health Technology Solutions (DHTS). For the study, a database will be developed and a dataset for the study without personal identifiers will be made available to the CDC upon request.

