### 7.1 Analysis Plan

**7.1.1 Study Populations** – There will be two study populations for this study. The Intent-to-Treat (ITT) and Safety populations. The ITT Population includes any participant that was enrolled and randomized into the study. The Safety Population is a subset of the ITT Population excluding those participants that never received the study intervention (either the influenza or Tdap vaccine). Statistical analyses will be performed for both study populations, or the ITT Population only if no participants are excluded for the Safety Population.

**7.1.2 Primary Objective 1** - To assess proportions of reactogenicity events in pregnant women receiving Tdap and IIV simultaneously vs. sequentially

Reactogenicity will be assessed for 7 days following each vaccination visit, as described in Section 5.3. The proportion of women and a 95% exact binomial confidence interval will be presented by treatment group, symptom, and grade level (mild/moderate/severe) for women with injection site reactogenicity within 7 days post-vaccination. This will be presented for each of the four reactogenicity outcomes, using the highest grade reported per woman. A 95% confidence interval of the difference in proportions between the treatment groups will also be presented. Systemic reactogenicity will be presented in a similar fashion. For adverse events, the proportion of women and a 95% exact binomial

confidence interval of adverse events, as well as the total number of adverse events, will be presented by treatment group, severity, and relatedness

**7.1.3 Primary Objective 2** - To assess maternal immune responses and cord blood antibody levels to pertussis antigens, tetanus and diphtheria toxoids, and influenza antigens in the women receiving Tdap and IIV simultaneously vs. sequentially

**7.1.3.1 Pertussis antigens** - Geometric mean titers (GMTs) will be calculated along with 95% confidence intervals for the two treatment groups for each pertussis antigen tested. A 95% confidence interval of the difference in GMTs between the treatment groups will also be presented.

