**Visit 1**

Post-Vaccination Day (Date (dd/MM/yyyy))	Day 1 (Day of vaccination)	Day 2	Day 3	Day 4	Day 5	Day 6	Day 7	Day 8
Oral Temperature °F	/ /	/ /	/ /	/ /	/ /	/ /	/ /	/ /
General Systemic Symptoms: Grade 0 = None								
Chills/Shivering	Grade 1 = Mild (noticeable but does not interfere with activity) Grade 2 = Moderate (interferes with activity but did not need a medical visit or absenteeism [i.e. missing work or school]) Grade 3 = Severe (prevents daily activity and/or resulted in medical visit and/or absenteeism [i.e. missing work or school])							
Fatigue								
Body Aches								
Headache								
Joint pain								
Nausea								
Vomiting								
Diarrhea								
Abdominal Pain								
Body rash								

CISA TDAP/IIV Data Collection Form  
Memory Aid Simultaneous Group  
TT07A

Subject ID: \_\_\_\_\_

Flu Vaccine Local Vaccination Site Reactions:  RIGHT ARM  LEFT ARM								
	Grade 0 = None							
	Grade 1 = Mild (noticeable but does not interfere with activity)							
	Grade 2 = Moderate (interferes with activity but did not need a medical visit or absenteeism [i.e. missing work or school])							
	Grade 3 = Severe (prevents daily activity and/or resulted in medical visit and/or absenteeism [i.e. missing work or school])							
Pain								
Tenderness								
Swelling- size (mm)	mm	mm	mm	mm	mm	mm	mm	mm
Redness- size (mm)	mm	mm	mm	mm	mm	mm	mm	mm
Tdap Vaccine Local Site Reactions:  RIGHT ARM  LEFT ARM								
	Grade 0 = None							
	Grade 1 = Mild (noticeable but does not interfere with activity)							
	Grade 2 = Moderate (interferes with activity but did not need a medical visit or absenteeism [i.e. missing work or school])							
	Grade 3 = Severe (prevents daily activity and/or resulted in medical visit and/or absenteeism [i.e. missing work or school])							
Post-Vaccination Day	Day 1	Day 2	Day 3	Day 4	Day 5	Day 6	Day 7	Day 8
Pain								
Tenderness								
Swelling- size (mm)	mm	mm	mm	mm	mm	mm	mm	mm
Redness- size (mm)	mm	mm	mm	mm	mm	mm	mm	mm

CISA TDAP/IV Data Collection Form  
Memory Aid Simultaneous Group  
TT07A

Subject ID: \_\_\_\_\_

Other symptoms			

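### Section 7.1.2 gives no injection-site comparison by vaccine site and does not say how the two sites and the two vaccination visits are combined into one highest grade per woman

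*Combined protocol and SAP*

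**What the plan says.** Section 7.1.2 (Primary Objective 1) is the whole analysis plan for injection-site reactions. Proportions with exact intervals "will be presented by treatment group, symptom, and grade level (mild/moderate/severe) for women with injection site reactogenicity within 7 days post-vaccination". The reduction rule follows: "This will be presented for each of the four reactogenicity outcomes, using the highest grade reported per woman". The between-arm estimate is then specified: "A 95% confidence interval of the difference in proportions between the treatment groups will also be presented". The four outcomes match the four rows of Table 3: pain, tenderness, swelling and redness. Vaccine site is not among the listed breakdowns, and no summary by site appears elsewhere in Section 7.

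The data are collected at a finer level:

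- Section 5.2.3 requires that the two vaccines not go into the same arm.
- The simultaneous group's Visit 1 memory aid (Appendix B) has a flu-site block and a separate block headed "Tdap Vaccine Local Site Reactions", each with the four items.
- The sequential group records the flu site after Visit 1 (Appendix C) and the Tdap site after Visit 4 (Appendix E).
- Under Section 5.3, the simultaneous group records no solicited injection-site reactions after Visit 4.

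**The concern.** Each woman is due one IIV and one Tdap injection. The most direct local test of co-administration compares the same vaccine's site with and without the other vaccine on the same day. The diaries support that contrast, but the plan does not ask for it.

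Section 7.1.2 can be read in two ways, and each has a problem. If the highest grade is taken over both sites and both vaccination visits, a change at one site can be hidden behind reactions at the other, and the result cannot show which vaccine's reactions changed. If results are shown by visit, Visit 1 compares women with two injections against women with one, and Visit 4 has no local comparator.

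This bears on the reason for the trial. Section 1.1 reports of two earlier studies in non-pregnant adults that "one of the studies demonstrated higher reports of injection-site pain after simultaneous administration". It also notes that the earlier database study had no data on injection-site pain that did not lead to a medical visit.

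**Working it through.** The plan states no expected reaction rate, effect size or power, so there is no figure of its own to reproduce. The check uses assumed rates to show how each reading behaves.

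**Inputs from the document.** Section 3.1 gives "approximately 80 healthy pregnant women" and allocation is 1:1, so about 40 per arm. The reaction rates and the within-woman correlation between sites are assumptions.

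**Reading 1: highest grade over both sites and both visits.** Let pI and pT be the probabilities of any pain at the IIV and Tdap sites. The chance of pain at either site is

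- independent sites: 1 − (1 − pI)(1 − pT)
- latent correlation 0.5: 1 − P(neither), from a bivariate normal
- complete overlap: max(pI, pT)

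Worked example, independent sites, pT = 70% in both arms, pI = 30% sequential and 50% simultaneous: 1 − 0.70 × 0.30 = 0.79 against 1 − 0.50 × 0.30 = 0.85. The difference is 6 points, although the IIV-site difference is 20. At correlation 0.5 the proportions are 0.733 and 0.778, a difference of 4.5 points.

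Merged difference in percentage points, simultaneous minus sequential:

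| Assumed rates, sequential → simultaneous | Site difference | Independent | Correlation 0.5 | Complete overlap |
|---|---|---|---|---|
| IIV 30→50, Tdap 60 in both | +20 | +8.0 | +6.6 | 0 |
| IIV 30→50, Tdap 70 in both | +20 | +6.0 | +4.5 | 0 |
| IIV 30→50, Tdap 80 in both | +20 | +4.0 | +2.6 | 0 |
| Tdap 60→80, IIV 30 in both | +20 | +14.0 | +16.4 | +20 |
| Tdap 70→90, IIV 30 in both | +20 | +14.0 | +17.3 | +20 |
| IIV 30→50 and Tdap 60→80 | +20 at each | +18.0 | +19.0 | +20 |
| IIV 5→15, Tdap 10 in both | +10 | +9.0 | +7.7 | +5.0 |
| IIV 40→55 and Tdap 60→45 | +15 and −15 | −0.8 | −1.3 | −5.0 |

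Dilution is strong when the rise is at the less reactive site and reactions are common. It is modest for rare reactions. It is small or absent when the rise is at the more reactive site or at both. Opposite shifts nearly cancel unless overlap is complete.

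**Reading 2: by visit.** Take IIV 40% and Tdap 60% with no effect of co-administration. At Visit 1 the sequential arm has one injection (40%) and the simultaneous arm two. The apparent excess is (1 − 0.60 × 0.40) − 0.40 = 0.76 − 0.40 = 36 points if independent, 28 points at correlation 0.5, and 0.60 − 0.40 = 20 points with complete overlap. None of it reflects an interaction between the vaccines.

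**Precision of a by-site comparison.** For 30% vs 50% with 40 per arm, the 95% half-width is 1.96 × √(0.3 × 0.7/40 + 0.5 × 0.5/40) = 1.96 × 0.107 = 0.21, or about 21 points.

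**The case against.** The strongest reply is that the per-woman summary answers the stated objective. Section 2 asks about reactions in women vaccinated simultaneously or sequentially, which is a comparison of regimens, and the worst grade per woman over the whole regimen is a legitimate measure of it. That stands, so the per-woman summary should keep its place.

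A reader might infer that the plan pools the two sites and therefore hides site-specific effects. The document does not say so. The highest-grade rule also reads naturally as the way to reduce eight daily diary entries to one value, and the same paragraph refers to each vaccination visit. Nor is hiding the general result: the 3-8 point figures apply to a rise at the less reactive site. Section 1.1 does not say which site had more pain in the earlier study, and the documents give no rates by site.

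A reader might also infer that sequential women who miss Tdap or the second diary add to the masking, because only one site then counts for them. The direction is the reverse: a lower sequential proportion widens an apparent excess in the simultaneous arm. Under the first three scenarios, 5% missing second diaries (the limit of the collection target in Table 6) would lower the sequential proportion by about 1.8-2.8 points; for example 0.05 × (0.72 − 0.30) = 2.1 points.

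Finally, Section 7 says: "This pilot study is not designed based on statistical considerations regarding power/sample size in relation to group comparisons". A by-site table will often be inconclusive, and it could be produced later from the stored data. Both points are fair and limit the consequence. They do not remove the gap: the plan still presents an interval for the between-arm difference in a primary outcome, and as written its meaning depends on an unstated rule.

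**Conclusion.** The concern holds as a gap in specification with a real effect on interpretation. Section 7.1.2 omits the like-for-like comparison by vaccine site and leaves undefined how sites and visits enter the per-woman grade. Under the merged reading, the share of a 20-point site effect that survives runs from none to all: about 3-8 points for the assumed IIV-site rise at independence or moderate correlation, zero there under complete overlap, and about 14-19 points for a rise at the Tdap site or at both, with no loss under complete overlap. Under the by-visit reading the error is upward, 20-36 points at the rates used. All of these sizes rest on assumed rates and correlations. What does not depend on them is that neither reading gives a like-for-like contrast that attributes a change to one vaccine's site.

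**What to change.** In Section 7.1.2:

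- Add, for each of the four symptoms, a comparison by vaccine site with the same exact intervals and interval for the difference: IIV site after Visit 1 in both arms, and Tdap site after Visit 1 (simultaneous) against after Visit 4 (sequential).
- Use as denominator the women who received that vaccine and returned that diary.
- Keep the highest-grade-per-woman summary beside these tables as the whole-regimen comparison, and state that it is taken over both sites and both vaccination visits.
- Label the added comparisons as descriptive.

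The cost is SAP wording and one extra set of descriptive tables. No new data are needed, because the memory aids already record each site.

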**Visit 4, Study Day 22 (window Days 22 – 29) Clinic Visit**

- For study participants in the sequential study group, review exclusion criteria listed in section 4.2 for Tdap vaccination
- Obtain vital signs including oral temperature prior to vaccination for study participants in the sequential group.
- Study staff will review the memory aid data and record any AEs, SAEs, concomitant medications, and current medical/pregnancy status as described in Section 5.1
- Obtain 15mL blood sample for serologic analysis (Section 6). Study participants in sequential group to have blood sample obtained prior to vaccination.
- For subjects in the sequential study group, trained, licensed research staff will administer Tdap as described in Section 5.2.3. Ensure participants receive Tdap Vaccine Information Sheets (VIS) during visit.
- Confirm subjects still have previously dispensed thermometer and ruler; if not, provide new supplies. Review instructions for use of thermometer, ruler, and memory aid (Appendix A) completion. All subjects will complete the memory aid (Appendix D and E) again to allow for the collection of “mock” data in the simultaneous group for comparison with the sequential group. Simultaneous group will only provide information for systemic reactions and oral temperature.

- Confirm preferred method of contact for follow-up (telephone or email reminder)
- Confirm date of next scheduled prenatal appointment

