### **5.2.1 Randomization**

Participants will be randomized (1:1) to receive either IIV and Tdap simultaneously or sequentially (IIV followed by Tdap) using a permuted block randomization scheme stratified by Lead and Contributing sites. The project statistician at Duke University will generate permuted block randomization schemes which will be uploaded to REDCap. The randomization schedule will not be available to the study staff, so the next randomization allocation will not be known before randomization occurs. Following confirmation of study eligibility criteria during Visit 1, participant randomization will be through REDCap with treatment allocation recorded on the CRF.

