### **5.2.2 Blinding**

This study will be open label and study staff and subjects will not be blinded. Laboratory and pathology staff will be blinded to treatment arm assignment.

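### Section 7.1.2 splits adverse events by an undefined, unblinded relatedness judgement and plans no between-arm interval, so the related-AE rows are liable to flatter simultaneous vaccination

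*Combined protocol and SAP*

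**What the plan says.** Section 7.1.2 (Primary Objective 1) treats reactions and AEs differently. For injection-site reactions it gives per-arm proportions and then adds: "A 95% confidence interval of the difference in proportions between the treatment groups will also be presented. Systemic reactogenicity will be presented in a similar". The last sentence of that quote, cut short here, gives systemic reactions the same treatment. For AEs it stops at per-arm results: the proportion of women and an exact 95% "confidence interval of adverse events, as well as the total number of adverse events, will be presented by treatment group, severity, and relatedness". Sections 7.1.5 and 7.1.6 again plan an interval of the difference, for birth outcomes and chorioamnionitis.

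The two arms share the same two diary weeks, one from Visit 1 and one from Visit 4. At Visit 4 the arms diverge: "For subjects in the sequential study group, trained, licensed research staff will administer Tdap as described in Section 5.2.3". The simultaneous arm gets no injection then but repeats the diary, "to allow for the collection of “mock” data in the simultaneous group for comparison with the sequential group". Table 2 schedules solicited and unsolicited AEs at Visits 1 to 6 without restricting them to one arm, and the simultaneous arm's Visit 4 memory aid (Appendix D) has a section for other symptoms with their intensity.

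On masking, Section 5.2.2 says: "This study will be open label and study staff and subjects will not be blinded". Only laboratory and pathology staff are blinded. Sections 5.3 and 5.4 do not define relatedness, name an assessor or set a time limit for it.

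**The concern.** The mock week gives the simultaneous arm a control period for background complaints, matched in time to the sequential arm's Tdap week. A split by relatedness can lose that match for AEs. A headache in the Visit 4 week comes within days of Tdap in one arm and at least three weeks after any vaccine in the other. An assessor who knows the arm and has no written rule has an obvious reason to call the first related and the second not.

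The related rows would then set two readily attributable weeks against one. The tilt has a predictable direction: towards simultaneous vaccination looking safer. Meanwhile the comparison that the matched weeks do support, AEs of any cause, gets no interval.

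These are two separate gaps. Putting an interval on the related rows would not repair the attribution problem.

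**Working it through.** **Inputs from the documents**
- Allocation (5.2.1): "Participants will be randomized (1:1) to receive either IIV and Tdap simultaneously or sequentially".
- Size (3.1): "This pilot study is a prospective, randomized open-label clinical trial of approximately 80 healthy pregnant women", so 80/2 = 40 per arm.
- Visit 4 falls on Day 22 to 29, which is 21 to 28 days after the Day 1 vaccination.
- No AE rate, relatedness rule or AE target is given, so there is no planned figure to reproduce.

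**Assumed quantities (not in the documents)**
- q: the chance, per woman and per post-injection week, of a background AE that is called related. It is a product, q = b × p, where b is the weekly chance of a background AE and p is the chance that such an AE is called related.
- r: attribution in the mock week relative to a post-injection week (0 = none, 1 = equal).
- g: the chance of a truly vaccine-caused AE, equal in both arms.

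**Women with at least one related AE**
- Sequential: 1 − (1 − g)(1 − q)²
- Simultaneous: 1 − (1 − g)(1 − q)(1 − rq)

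With no vaccine effect (g = 0) and no mock-week attribution (r = 0):

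| q | Sequential, 1 − (1 − q)² | Simultaneous, q | Gap (points) |
|---|---|---|---|
| 0.02 | 4.0% | 2.0% | 2.0 |
| 0.05 | 9.8% | 5.0% | 4.8 |
| 0.10 | 19.0% | 10.0% | 9.0 |
| 0.20 | 36.0% | 20.0% | 16.0 |

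At q = 0.10 this is 0.19 × 40 = 7.6 women against 0.10 × 40 = 4.0.

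**Sensitivity at q = 0.10**
- r = 0.5: simultaneous = 1 − 0.90 × 0.95 = 14.5%, against 19.0%; gap 4.5 points.
- r = 1: both arms 19.0%; gap 0.
- g = 0.20, r = 0: 1 − 0.80 × 0.81 = 35.2% against 1 − 0.80 × 0.90 = 28.0%; gap 7.2 points.
- If no background event is misattributed (q = 0), the gap is 0 whatever g is.

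**How small q may be.** If b = p = 0.1, then q = 0.01 and the rows read 1 − 0.99² = 2.0% against 1.0%. If b = p = 0.3, then q = 0.09 and they read 1 − 0.91² = 17.2% against 9.0%.

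**Would an interval on related AEs help?** No. With 40 per arm, q = 0.10, r = 0 and g = 0, full binomial enumeration with the Newcombe interval shows that a 95% interval of the difference would wrongly exclude zero in favour of the simultaneous arm in about 20% of trials.

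**Any-cause comparison.** With weekly background chance b and no true difference, both arms have 1 − (1 − b)² over the two weeks. At b = 0.10 that is 19.0% in each, and the interval wrongly excludes zero about 2.5% of the time on each side.

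**The case against.** Four counter-arguments have force.

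- **No bar on mock-week attribution.** A reader might infer that an event in the mock week cannot be called vaccine-related. Nothing in the documents says so. No time limit is set, calls to participants who cannot be reached continue to about Day 45, and Section 5.4 monitors medically attended events and SAEs from vaccination through delivery. The contact rule is not a causality rule, so it does not remove the asymmetry, but such events are only less likely to be called related.
- **The main use of the mock data is intact.** A reader might infer that the relatedness split undermines the mock week altogether. It does not. Solicited systemic reactions are graded in Table 4 without a causality filter and already have an interval of the difference.
- **No formal comparison of related AEs is planned.** This is correct, and AEs are a supporting summary placed under an objective about reactogenicity. Side-by-side arm columns will still be read across.
- **This is a descriptive pilot.** Section 7 says: "This pilot study is not designed based on statistical considerations regarding power/sample size in relation to group comparisons". That excuses the absence of tests and power. It does not explain why AEs lack the difference interval that the plan gives to its other arm outcomes.

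It is also fair to say that an any-cause count still rests on open-label self-report.

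**Conclusion.** The point holds as a moderate one about specification and interpretation; no stated figure in the plan is wrong. Section 7.1.2 omits a between-arm interval for AEs. Its relatedness split rests on an undefined judgement by unblinded staff, across arms with unequal numbers of post-injection weeks.

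The related-AE rows are liable to favour simultaneous vaccination. It would go too far to say that they are inflated. That requires background events to be called related, and more often after an injection than in the mock week.

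The size rests entirely on assumed values: with no mock-week attribution, 2 to 16 points for q from 0.02 to 0.20; 4.5 points at q = 0.10 with half the attribution; zero with equal attribution. A reader who takes q to be the chance that a given AE is called related would overstate the gap, because that chance must first be multiplied by the weekly chance of having an AE.

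**What to change.** In Section 7.1.2:

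- Make the between-arm AE comparison the proportion of women with at least one unsolicited AE of any cause over the two matched diary weeks (after Visit 1 and after Visit 4), overall and moderate-or-worse, with a 95% confidence interval of the difference.
- Leave solicited reactions in their own analysis. Section 5.3 counts them as adverse events, so the AE definition should exclude them explicitly.
- Summarise later medically attended events and SAEs separately.
- Keep relatedness as a descriptive within-arm summary, with a table note that mock-week events are less likely to be judged related and that these rows should not be compared between arms.

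A sentence in Section 5.4 saying who judges relatedness, and by what rule in both arms, would make the descriptive rows easier to read. It would not replace the any-cause comparison.

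The cost is SAP wording and a few table rows on data already collected. The downside is that related AEs are no longer read as an arm comparison, and self-report remains open label.
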